#### **4.3. Subject Discontinuation from Investigational Product**

The subject must be discontinued from IPs in the event of any of the following:

- Consent withdrawal by subject
  - If subjects withdraw his/her consent, Investigator must inquire the reasons for consent withdrawal as to whether it is related to the study (e.g., documented lack

of efficacy, AE or pregnancy); however, the subject could refuse to provide such reason

- If the main reason for consent withdrawal is considered related to the study, the Investigator may select appropriate reason among the reasons listed below other than consent withdrawal
- Rhegmatogenous retinal detachment or full-thickness macular hole in the study eye
- Any newly developed or aggravated ophthalmic abnormality other than AMD in the study eye which could interfere with evaluation of efficacy or safety of IP including but not limited to retinal vascular abnormality
- Any AEs in the study eye (e.g., intraocular inflammation, VA loss, increased IOP, subretinal haemorrhage, vitreous haemorrhage, local or systemic infection etc.) which in the opinion of the Investigator and/or subject would require IP discontinuation
- Intraocular surgery in the study eye (e.g., cataract operation, vitrectomy, glaucoma surgery, etc.) which in the opinion of the Investigator would require IP discontinuation
- Protocol deviations which may adversely affect the subject's safety and/or integrity of data as agreed by the Investigator and/or upon request from the Sponsor
- IP non-compliance
  - A subject misses any of first two doses (ITV injection of IP at Week 0 (Day 1) and Week 4) after randomisation
  - A subject misses two consecutive doses during the study period after randomisation
- Decision by the Investigator that the subject requires alternate treatment (e.g., other anti-VEGF agents such as bevacizumab or aflibercept, PDT, PPV etc.) to treat neovascular AMD in the study eye
- Decision by the Sponsor that IP discontinuation is in the subject's best medical interest or administrative decision for a reason (e.g., a suspicion of fraud, the subject enrolling in multiple clinical studies, lack of compliance, etc.) other than that of an AE
- Lost to follow-up
- Unmasking (except unmasking for the purpose of regulatory reporting)

- Pregnancy
- Death of any cause

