Any significant change in the posterior pole (e.g., subretinal haemorrhage, macular hole, vitreous haemorrhage or opacity, retinal detachment, etc.) that is detected with fundus examination should be confirmed and documented with FP and/or FA. Investigator should decide IP discontinuation based on the FP and/or FA. The images taken at unscheduled visits will not be sent to the central reading centre.

If a subject is prematurely discontinued from IP due to any of the above described reasons excluding death, the subject will complete the ET procedures (except for PK sampling) after 4 weeks from the last ITV injection of IP and will be asked to provide continued follow-up and further data collection subsequent to his or her ET visit.

If a subject agrees to continue follow-up for associated clinical outcome information until Week 52 irrespective of IP injection status (as long as an additional ICF e.g., withdrawal form is signed by the subject for this limited participation in the study), the subject's clinical outcome information such as BCVA, CST, AE and concomitant medication will be collected through non-invasive chart review, if available.

If a subject does not agree to continue follow-up of associated clinical outcome information, the subject will be terminated from the study accordingly. The data and blood samples collected on the subject up to ET visit remains in the study database and no further data will be collected.

In all cases, the reason for IP discontinuation must be recorded in the electronic Case Report Form (eCRF) and in the subject's medical record.

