## **5. TREATMENT AND INVESTIGATIONAL PRODUCT**

### **5.1. Treatment of the Subjects**

#### **5.1.1. Dosing and Treatment Schedule**

Subjects will be administered SB11 or Lucentis® 0.5 mg via ITV into the study eye every 4 weeks up to Week 48 (a total of 13 administrations of IP) unless they are early discontinued from IP.

IP injection will be performed by the Investigator according to delegation of study personnel for this study.

Dosing visits will be allowed within  $\pm 7$  days of the scheduled dosing visit date (except Week 0 (Day 1), visit window not allowed). If a dose of IP is not given within 7 days of the scheduled dosing visit date, the IP should be given within 20 days of the scheduled dosing visit date, but the case will be captured as protocol deviation. Dosing skip is defined when a subject does not receive the IP within 20 days after scheduled dosing visit date.

Next scheduled dosing visit date and visit window should not be altered even though previous dosing is not performed on the exact scheduled dosing visit date (but, the interval between two doses injected into the study eye should be at least 14 days) or previous dosing is skipped.

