### **9.2.2. Efficacy**

For US FDA, Korea MFDS or other regulatory agency submissions for those who are in favour of the VA, the primary efficacy analysis will be performed for the FAS with the change from baseline of BCVA at Week 8 using an analysis of covariance model with the baseline BCVA as a covariate and region (or pooled centres) and treatment group as factors. The equivalence in BCVA will be declared if the two-sided 90% Confidence Interval (CI) of the difference in terms of BCVA Least Squares mean (LS mean) changes from baseline at Week 8 between SB11 and Lucentis® lies within the pre-defined equivalence margin of [-3 letters, 3 letters].

For EMA or other regulatory agency submissions for those who are in favour of the anatomical parameter, the primary efficacy analysis will be performed for the per-protocol set (PPS-CST) with the change from baseline of CST at Week 4 using an analysis of covariance model with baseline CST as a covariate and region (or pooled centres) and treatment group as factors. The equivalence in CST will be declared if the two-sided 95% CI of the difference of the CST LS mean changes from baseline in Week 4 between SB11 and Lucentis® lies within the pre-defined equivalence margin of [-36 µm, 36 µm].

No formal adjustment of Type I error rates will be performed.

For the primary analysis with the FAS for BCVA, missing data will be imputed for subjects who drop out for the study prior to the primary analysis time-point. A missing-at-random approach will assume that subjects who withdraw from a study had missing values similar to similar subjects who completed the study in that treatment group. This approach ensures that evidence of lack of equivalence is not diluted when there are missing data. For the components of BCVA, the missing letter will be imputed by multiple imputation method with the assumption of monotone missing pattern and regression method. For the sensitivity analyses, available case analysis and last observation carried forward analysis will be performed.

All other secondary efficacy measurements will be summarised descriptively by treatment group and visit, and analysed using analysis of covariance model for continuous outcomes or Cochran-Mantel-Haenszel method for categorical outcomes unless otherwise specified.

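### Does the primary BCVA analysis drop a FAS subject who stays in the study but has no Week 8 value?

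*Combined protocol and SAP*

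**What the plan says.** Section 9.2.2, repeated in the Synopsis, introduces imputation with the words "missing data will be imputed for subjects who drop out for the study prior to the primary analysis time-point". The missing-at-random assumption is likewise phrased for withdrawals: "subjects who withdraw from a study had missing values similar to similar subjects who completed the study in that treatment group". The method sentence then provides for a "multiple imputation method with the assumption of monotone missing pattern and regression method", and it carries no restriction to drop-outs. Available-case and last-observation-carried-forward analyses are the two sensitivity analyses.

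Section 9.1 makes the FAS the primary set for BCVA. It comprises all randomised subjects under intention-to-treat, apart from subjects randomised in error and never dosed.

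Section 4.3 separates stopping the product from leaving the study. A subject off product has the early termination visit and may agree to further follow-up, provided that a "withdrawal form is signed by the subject for this limited participation in the study". For such a subject, "clinical outcome information such as BCVA, CST, AE and concomitant medication will be collected through non-invasive chart review, if available". Only for those who refuse does it say: "If a subject does not agree to continue follow-up of associated clinical outcome information, the subject will be terminated from the study accordingly".

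On missed doses, Section 4.3 requires discontinuation after a missed Week 0 or Week 4 dose, or when "A subject misses two consecutive doses during the study period after randomisation". Section 5.1.1 adds that "Next scheduled dosing visit date and visit window should not be altered" because an earlier dose was late or skipped. Section 9 leaves further statistical detail to a SAP to be finalised before the database lock for the main report.

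**The concern.** The sentence that opens the imputation rule describes people who leave the study, and the protocol allows two kinds of subject who do not leave yet have no Week 8 BCVA.

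1. A subject who misses only the Week 8 visit. One missed dose at Week 8 does not trigger discontinuation, and the schedule simply resumes at Week 12.
2. A subject taken off product before the Week 4 dose, who agrees to follow-up and has no usable BCVA in the chart near Week 8.

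Read word for word, neither is imputed. The analysis labelled FAS would then omit randomised subjects for a reason arising after randomisation. The available-case sensitivity analysis would omit the same subjects and so could not show the effect. In an equivalence trial, losing subjects whose outcomes differ by arm can pull the estimate toward zero and make equivalence easier to declare.

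**Working it through.** **1. Which reading fits the section.** The word only does not appear in the imputation sentence. The method sentence speaks of the missing letter without qualification, and the aim given just before it, keeping evidence against equivalence from being diluted, concerns missing data in general. If the primary analysis ignored missing values in subjects still under follow-up, it would be an available-case analysis for them, yet the section lists available-case separately as a check on the primary result. The coherent reading is that every FAS subject without a Week 8 value is imputed.

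**2. Whether the stated method can do it.** A subject with baseline and Week 4 BCVA and no Week 8 value has the last item in the sequence missing. That pattern is monotone for data up to Week 8, so the stated regression method applies as it stands. A gap at Week 1 with Week 4 present would break monotonicity only if Week 1 were a predictor, and the protocol does not list predictors.

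**3. How many subjects can be affected.**
- *Off product.* Section 7.16 puts the early termination visit, which includes BCVA, 4 weeks (± 7 days) after the last injection. A subject whose last injection was on schedule at Week 4 (Day 29) is seen at about Day 29 + 28 = Day 57, the scheduled Week 8 day. The gap is therefore confined essentially to subjects who never received the Week 4 dose, agreed to follow-up, and have no chart BCVA. Section 4.3 gives a withdrawal form as its example of the extra consent, and Section 8.1.8 speaks of subjects withdrawn for an adverse event who are still followed. The protocol's use of withdraw can thus include this group.
- *Lone missed Week 8.* Table 1 (footnote 8) and the note in Section 7.1 single out Week 8 as critical. BCVA is taken before injection (Section 6.2.1), so a skipped injection alone does not create the gap. A dose more than 7 days late may still be given up to 20 days after the scheduled date, as a protocol deviation.
- The documents give no rate. As an assumption, let these subjects be 0% to 100% of the planned 5% loss. Then 0 to 704 × 0.05 = 35 subjects are affected, and 7 if they make up one fifth.

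**4. Power.** Inputs from Section 9.3: margin 3, true difference 0.5, SD 12.5. The 90% CI rule in Section 9.2.2 corresponds to two one-sided 5% tests.

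SE = 12.5 × √(2/n); power = Φ((3 − 0.5)/SE − 1.645) + Φ((3 + 0.5)/SE − 1.645) − 1.

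| Contributing per arm | SE | Power |
|---|---|---|
| 333 (smallest n reaching 80%) | 0.969 | 80.1% |
| 334 (plan's completers) | 0.967 | 80.2% |
| 352 (all randomised) | 0.942 | 82.4% |

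The plan's figure reproduces (334 stated, 333 minimum), and 334/0.95 rounds up to 352. Because 334 already excludes the whole 5%, leaving these subjects out costs nothing against the stated 80%. If they came on top of the 5%, an extra 1% to 5% missing (330 to 316 per arm) would give 79.7% to 77.7%.

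**5. Bias on the literal reading.** Assume that the chance of a Week 8 gap is proportional to exp(−z), with z the standardised Week 4 BCVA, and that Week 4 and Week 8 correlate at ρ = 0.6 to 0.9. Under normality the missing subjects average z = −1, so their Week 8 mean lies 12.5ρ letters below the arm mean. Leaving out a share f shifts the mean of the rest by f/(1 − f) × 12.5ρ. With f = 1% (3.5 of 352):
- ρ = 0.6: (0.01/0.99) × 7.5 = 0.076 letter
- ρ = 0.9: (0.01/0.99) × 11.25 = 0.114 letter

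That is 2.5% to 3.8% of the 3-letter margin. Regression imputation on Week 4 removes nearly all of it; in simulation the residual was at most 0.002 letter. If both arms lose the same share for the same reason, the shift cancels in the treatment difference.

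**6. Effect on the error rate.** Suppose the loss is in one arm only, the true difference is exactly 3 letters, and the bias runs toward zero. One-sided error = Φ(−1.645 + bias/0.942), which gives 5.9% at 0.076 and 6.4% at 0.114, against 5%.

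**The case for a change.** The best case for a change is that Section 4.3 itself distinguishes stopping the product from leaving the study and keeps termination from the study for those who refuse follow-up. Against that background, an imputation sentence framed around leaving the study admits two readings of who enters the primary equivalence analysis. That choice should be fixed before unmasking, and fixing it would cost one sentence in two places. The literal reading also sits awkwardly with the protocol's claim that its approach avoids diluting evidence against equivalence.

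Part of this stands. No sentence expressly covers these subjects, and a SAP that says the rule applies to Week 8 BCVA missing for any reason would be clearer. It does not make the protocol wrong. The FAS definition, the unrestricted method sentence and the separate available-case analysis all point the same way. The SAP, due before database lock, is where the imputation model and its scope are normally written out, and no separate SAP text is among the documents to show otherwise. Last observation carried forward also keeps any subject with an earlier BCVA, so one of the two sensitivity analyses would show whether exclusion mattered.

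**Conclusion.** The concern identifies an unstated detail that analysts would fill sensibly, so no change to the plan follows. The text omits an express rule for a Week 8 gap in a subject still in the study, but its structure supports imputing that subject, and the stated monotone regression method can do so for a lone Week 8 gap. On the least favourable wording, the 80% power is intact unless such gaps come on top of the planned 5% loss. The bias is about 0.08 to 0.11 letter per 1% lost in one arm, against a 3-letter margin. The bias figures rest on assumed missingness and an assumed Week 4 to Week 8 correlation of 0.6 to 0.9, and they do not use the baseline adjustment in the ANCOVA. The number of affected subjects is unknown, and the visit rules make it likely to be small.

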#### **6.1.2. Secondary Endpoints**

**The secondary efficacy endpoints are:**

- Change from baseline in BCVA over time up to Week 24 and Week 52
- Proportion of subjects who lost fewer than 15 letters in BCVA compared to baseline at Week 24 and Week 52
- Proportion of subjects who gained 15 letters or more in BCVA compared to baseline at Week 24 and Week 52
- Change from baseline in CST and Central Retinal Lesion Thickness (CRLT) at Week 24 and Week 52 (based on assessment by central reading centre)
- Change from baseline in total CNV size at Week 24 and Week 52 (based on assessment by central reading centre)
- Proportion of subjects with active CNV leakage at Week 24 and Week 52 (based on

assessment by central reading centre)

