**6.1.3. Exploratory Endpoint**

- Proportion of subjects without intra- or sub-retinal fluid at Week 24 and Week 52 (based on assessment by central reading centre)

The Quality of Life (QOL) is assessed using National Eye Institute 25-Item Visual Function Questionnaire (NEI VFQ-25).

- Change from baseline in subscale scores and composite scores of NEI VFQ-25 at Week 24 and Week 52

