## **9.2. Statistical Methods and Analytical Plan**

### **9.2.1. Demographics and Baseline Characteristics**

Subject demographics and baseline characteristics will be summarised by treatment group for the RAN and PKS. Continuous variables (e.g., age, weight, height) will be summarised with descriptive statistics (n, mean, SD, median, minimum, maximum) and categorical variables (e.g., gender, race, ethnicity) will be summarised with frequency and percentage.

Comparison between treatment groups in baseline characteristics will be performed using the chi-square test or F-test as appropriate. The results of these tests will be provided including the p-value only for descriptive purposes and will not be used as a formal basis to determine the factors to be included in primary or secondary efficacy analysis models. If baseline imbalances are detected for any of the factors, additional analyses may be performed to adjust for these baseline differences.

Relevant medical history will be summarised by treatment group for the RAN.

Duration of exposure to IP and number of injections will be summarised by treatment group with descriptive statistics for the SAF. Prior and concomitant medications and significant non-drug therapies will be summarised by treatment group with frequency and percentage.

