#### **9.2.6. NEI VFQ-25**

Subscale scores (general health, general vision, ocular pain, near activities, distance activities, vision-specific social functioning, vision-specific mental health, vision-specific role difficulties, vision-specific dependency, driving, colour vision, and peripheral vision) and the

composite score, which represent overall visual function, will be calculated, and the change from baseline will be summarised by treatment group and visit.

In addition, the subscale scores and composite score of NEI VFQ-25 will be also summarised without subjects who received Lucentis® in the fellow eye due to AMD during the study period after randomisation.

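### The 15-letter gain and loss endpoints go to Cochran-Mantel-Haenszel with no stratum named, so as written they do not use baseline BCVA, unlike the primary BCVA analysis

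*Combined protocol and SAP*

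**What the plan says.** Section 9.2.2 analyses the Week 8 BCVA change with an "analysis of covariance model with the baseline BCVA as a covariate and region (or pooled centres) and treatment group as factors". One sentence covers the other secondary efficacy outcomes: they are summarised by arm and visit and "analysed using analysis of covariance model for continuous outcomes or Cochran-Mantel-Haenszel method for categorical outcomes unless otherwise specified". It lists no covariates for the secondary ANCOVA and no strata for CMH.

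Two secondary endpoints in Section 6.1.2 are thresholds on BCVA change: "Proportion of subjects who lost fewer than 15 letters in BCVA compared to baseline at Week 24 and Week 52" and "Proportion of subjects who gained 15 letters or more in BCVA compared to baseline at Week 24 and Week 52".

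Three other places bear on the point:
- Section 9.2.1 provides that "If baseline imbalances are detected for any of the factors, additional analyses may be performed to adjust for these baseline differences".
- The opening of Section 9 leaves further method detail to a SAP finalised before the database lock for the main report. The documents in hand contain no such further text on this point.
- The synopsis, under Statistical Methods, plans only descriptive summaries for efficacy measures other than the primary ones, which differs from Section 9.2.2.

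**The concern.** Mean BCVA change and the 15-letter proportions come from the same letter scores and will be read side by side as supportive evidence of similarity. Entry BCVA may lie anywhere from 34 to 73 letters (inclusion criterion 5), so baseline plausibly predicts who crosses a 15-letter threshold. CMH cannot take a continuous covariate, and no baseline category is named as a stratum.

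If the arms differ by chance at baseline, a baseline-adjusted mean-change analysis allows for it, but the comparison of proportions as written does not. The two summaries could then drift apart for a reason unrelated to the products. Some precision available from a value already collected is also given up. What is at stake is the coherence and precision of secondary comparisons, not the equivalence conclusion.

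**Working it through.** **1. The plan's own figure.** No figure in the plan attaches to the gain or loss endpoints. The figure that could be affected is the BCVA sample size, and it reproduces. Inputs from Section 9.3 are margin 3, true difference 0.5, SD 12.5 and a 90% CI (one-sided 5% per test). The standard error at 334 per arm is 12.5 × √(2/334) = 0.967. Two one-sided t tests then give 80.1% power, and 334 is the smallest number reaching 80%. Allowing for 5% loss, 334/0.95 = 351.6, so 352 per arm and 704 in total. None of this involves the gain or loss endpoints.

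**2. Baseline width of the intervals.** As illustrative rates I take the MARINA Month 12 row of Table 3 (0.5 mg arm): 31% gaining 15 letters and 91% losing fewer than 15. With 352 per arm, the 95% half-width is 1.96 × √(2p(1−p)/352):
- gain: 1.96 × 0.0349 = 6.83 percentage points
- loss: 1.96 × 0.0216 = 4.23 percentage points

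**3. What baseline adjustment would save.** The variance of a standardised, baseline-adjusted difference is about (1 − R²) times the unadjusted variance, where R² is the share of outcome variance explained by baseline. The documents do not give R². I derived it from an assumed correlation r between baseline BCVA and BCVA change, with mean change 6.3 and SD 14.1 (same MARINA row). Baseline was drawn from a normal distribution with mean 58 and SD 10 (assumed), cut to 34–73.

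| Assumed r | R², gain | CI narrower, gain | R², loss | CI narrower, loss |
|---|---|---|---|---|
| -0.2 | 0.023 | 1.2% | 0.010 | 0.5% |
| -0.3 | 0.054 | 2.7% | 0.023 | 1.2% |
| -0.4 | 0.097 | 5.0% | 0.041 | 2.1% |

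A direct simulation of standardised logistic regression for gain (1,500 trials per correlation, 335 per arm, mean change 8, SD 13, baseline SD about 9, all assumed) gave variance ratios of 0.985, 0.955 and 0.912. Taking 1 − √ratio, the interval is 0.8%, 2.3% and 4.5% narrower. In points, for R² of 0.02, 0.05 and 0.10, the gain half-width goes from 6.83 to 6.76, 6.66 and 6.48. For loss, R² of 0.04 takes 4.23 to 4.23 × √0.96 = 4.14.

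**4. Effect of a chance imbalance on the gain endpoint.** Use 335 per arm, baseline SD 10, mean change 8 and SD 13 (all assumed). The 95% limit of a chance baseline difference is 1.96 × 10 × √(2/335) = 1.51 letters. The slope of change on baseline is r × 13/10, so the expected change differs by 0.39, 0.59 and 0.79 letters for r of -0.2, -0.3 and -0.4. With P(change ≥ 15) = 29.5%, the unadjusted difference moves by about 1.0, 1.5 and 2.1 percentage points. The baseline SD cancels between imbalance and slope, so an SD of 9 gives the same shifts.

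**The case against.** The strongest reply is that silence is not exclusion. CMH is a stratified method and no strata are listed at all, not even region. The sentence allows for other specification, and a later SAP may supply it. The secondary ANCOVA lists no covariates either. This stands in part: a reader might infer that the plan rules out baseline BCVA for the gain and loss endpoints, and the text does not say that. It leaves the strata unnamed, which is still a gap to close before unmasking.

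Section 9.2.1 also leaves room for adjusted analyses. That room is optional, opens only once an imbalance has been seen, and names no model, so it does not replace a pre-specified analysis.

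Two stronger readings are tempting, and the documents do not support them:
- A reader might say the baseline values go unused. They do not, because gain and loss are computed from baseline. What is missing is baseline as a covariate or stratum.
- A reader might extend the point to NEI VFQ-25, for which "the change from baseline will be summarised by treatment group and visit". Section 6.1.3 lists it as exploratory, and no between-arm contrast, margin or test is planned. There is no comparison whose precision is lost, and keeping it descriptive is legitimate.

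The size objection stands too. The saving is a fraction of a percentage point in half-width. The shifts in step 4 need an imbalance at its 95% limit, and the unadjusted interval already counts chance imbalance as sampling error. A mean and a threshold proportion can also diverge for reasons that have nothing to do with baseline.

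**Conclusion.** The point holds as a minor, worthwhile improvement. As written, the 15-letter gain and loss comparisons at Weeks 24 and 52 do not use baseline BCVA as a covariate or stratum, whereas the primary BCVA analysis does. For gain, adjustment would lower the variance by about 2% to 9% and narrow the interval by about 1% to 5%. For loss, the benefit is about 2% of interval width at most. The more useful result is coherence: under a chance imbalance, the proportions would move with a baseline-adjusted mean change.

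These figures rest on assumed correlations of -0.2 to -0.4 and assumed baseline distributions, and the 335 or 352 per arm used here are not stated numbers for Weeks 24 or 52. The endpoints have no margin, power statement or equivalence criterion, so no decision rule of the trial depends on this.

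**What to change.** In the SAP, before unmasking for the main report:
- For gain and loss at Weeks 24 and 52, pre-specify logistic regression with treatment, region and continuous baseline BCVA. Standardise it over the analysis set to give the SB11 minus Lucentis difference in proportions with its CI.
- Keep CMH as a supportive analysis and name its strata, for example region.
- State the covariates of the secondary ANCOVA, so that mean change and proportions are adjusted alike.
- Reconcile the synopsis with Section 9.2.2 on whether secondary efficacy endpoints are compared or only described.
- Leave NEI VFQ-25 descriptive. Only if a between-arm difference is to be reported, take it from ANCOVA with the baseline score as covariate.

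The cost is a few lines of text and code. No new data are needed, and the primary tests and the 704 subjects stay as they are.
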